### List of Abbreviations

AE	Adverse Event/Adverse Experience
CFR	Code of Federal Regulations
CRF	Case Report Form
CTCAE	Common Terminology Criteria for Adverse Events
DSMB	Data and Safety Monitoring Board
FDA	Food and Drug Administration
GCP	Good Clinical Practice
HIPAA	Health Insurance Portability and Accountability Act
IB	Investigator's Brochure
IND	Investigational New Drug Application
iPSC	Induced Pluripotent Stem Cells
IRB	Institutional Review Board
NSCLC	Non-Small Cell Lung Cancer
PHI	Protected Health Information
PI	Principal Investigator
RFS	Recurrence Free Survival
SAE	Serious Adverse Event/Serious Adverse Experience
SCC	Squamous Cell Carcinoma
SOP	Standard Operating Procedure

## Study Summary

Title	A pilot study of metformin as a chemoprevention agent in non-small cell lung cancer
Running Title	A pilot study of metformin as a chemoprevention agent in non-small cell lung cancer
Protocol Number	12-006865
Phase	Phase II-Pilot study
Methodology	Patients will be identified and enrolled from Thoracic Surgical Clinics. Patients will undergo surgical resection with the collection of tumor tissue, normal lung, blood, and skin biopsies. For patients enrolled in the study that were found to have stage IA-IIIA SCC, starting less than 90 days from the time of surgery, patients will be randomized to receive either 850 mg po BID of metformin or observation. Metformin dosing will include a 4 week ramp up of 850 mg po daily prior to starting the BID dose, for a total of 6 months of Metformin. Patients will be followed for 2 years from the time of surgery to evaluate 2-year Recurrence Free Survival.
Overall Study Duration	08/01/2012 to 07/30/2017
Subject Participation Duration	2 Years
Single or Multi-Site	Single Site
Objectives	
 
1. To evaluate the feasibility of patient randomization, accrual, and tissue collection in a pilot study of metformin versus observation following resection of stage IA-IIIA lung squamous cell cancer for patients.
 
2. To compare the 2-year recurrence free survival rate between metformin and observation.
 

Number of Subjects	100
Diagnosis and Main Inclusion Criteria	Suspected or biopsy proven Stage IA-IIIA NSCLC (must be proven squamous cell carcinoma at the time of surgery)medically fit for surgical resection (based on surgeon assessment), current or prior smoker, age >18, no existing untreated or prior cancer <5 years from diagnosis, willing and able to consent to study, undergo study interventions, and take study drug; not diabetic or currently taking metformin or other diabetic drug, ECOG performance status 0,1, or 2.
Study Product, Dose, Route, Regimen	Metformin dosing will include a 4 week ramp up of 850 mg po daily prior to starting the BID dose.
Duration of Administration	Six Months

Reference therapy	Observation
-------------------	-------------

## Introduction

Insufficient data for the feasibility of enrolling lung cancer patients to a trial protocol of metformin versus placebo with concurrent collection of biospecimens raises questions regarding the potential of performing a large, randomized, phase III study. The proposed pilot study will collect data to demonstrate the potential for enrolling patients to such a protocol, assess the feasibility of performing the study using the CCOP mechanism, collecting biospecimens from patients on study, and generate preliminary data to assess if a large, randomized, phase III study is indeed feasible and justified.

Metformin is a widely prescribed oral medication used as front-line therapy for type 2 diabetes. It has been shown to inhibit the growth of cancer cell lines, including breast cancer, in vitro and in vivo tumor models. Population and retrospective studies showed that metformin decreases the incidence of cancer and cancer-related mortality, and increases the response to neoadjuvant chemotherapy in diabetic patients. As a result, metformin is being investigated as a therapeutic agent in different clinical settings for many cancer subtypes. Evidence for an anti-cancer effect in NSCLC would justify its use as a preventative agent in the patient with treated disease. Successful execution of the correlative studies described will increase understanding of genomic changes in the precursor lesion bronchial dysplasia, and reveal potential therapeutic targets to prevent disease progression.

Phase I/II studies directed toward effects on existing tumors or pre-invasive lesions with surrogate endpoints have shown promise, but may not translate to real effects on the histologically normal tissue and cell types that are the true targets of chemoprevention. Our recent in vitro data indicating heterogeneity in metformin response suggest that all patients may not respond equally to its potential chemoprevention effects. The preliminary data to be gathered in the proposed pilot study will be critical to evaluate the feasibility of performing a randomized, phase III trial addressing this question as an Alliance study through the cooperative group infrastructure. The pilot data will also serve as important preliminary data for a correlative studies R01 grant in conjunction with a larger trial, with aims of evaluating the effects of metformin on patients with resected Stage IB-IIIA NSCLC, creating cohorts of metformin responders and non-responders based on disease recurrence, and finally generating iPS cells for in vitro studies and development of a metformin response index. This pilot trial will also address an under-represented area (lung cancer) in the Alliance Prevention Committee portfolio.

### 1.1 Background

#### Non-small cell lung cancer (NSCLC)

Worldwide, lung cancer remains the leading cause of cancer-related death in men and the second leading cause of cancer-related deaths in women (Jemal et al., 2011). The American Cancer Society estimates an incidence of 221,130 new cases of lung cancer for 2011 with 156,940 deaths (Siegel et al., 2011). Non-small cell lung cancer (NSCLC) accounts for more than 80% of all pulmonary neoplasms with greater than 60% of patients presenting with advanced or metastatic disease at the time of diagnosis [SEER; Little 2007]. Despite having a better chance for cure following surgical resection, even patients with early stage disease have a relatively high

risk of recurrence, with reported local recurrence rates ranging from 13% to 45% for Stage I disease and 17% to 55% for Stage II disease [Kelsey 2009, Lardinois 2005, Goodgame 2009]. Despite advances in screening, targeted therapies, adjuvant chemotherapy, minimally invasive surgery, and stereotactic radiation, the overall approach to lung cancer care has changed little in over 25 years, with relatively minimal improvements in survival.

#### Metformin as a chemoprevention agent

Metformin is an insulin sensitizer commonly used to treat diabetes. It lowers serum insulin levels and also directly inhibits cell growth. In addition to inhibiting gluconeogenesis, it also activates AMP kinase in epithelial cells by an LKB dependent mechanism. AMP kinase activation suppresses cell proliferation in malignant and nonmalignant cells by two different pathways -- inhibition of mTOR as well as through upregulation of p53/p21. Metformin may exert anti-tumour effects through both insulin dependent and insulin-independent mechanisms. Metformin also has indirect anti-proliferative effects related to lower systemic levels of insulin. The drug is well tolerated even by individuals without diabetes and does not cause hypoglycemia. Its main limited side effects are transient nausea and diarrhea. Lactic acidosis, a major adverse effect, is rare and seen only in those with concomitant renal failure or liver disease. Recent studies have shown its potential as a cancer prevention drug in cancers such as breast, prostate, pancreas, and colon.

In observational epidemiologic work, Evans et al. reported the risk of subsequent cancer diagnosis (all cancer types) was reduced in type 2 diabetics who received metformin (OR 0.85 for any vs. no metformin exposure). The protective effect increased with greater metformin exposure (measured as total dose prescribed or total duration of use). Additionally, Bowker et al. reported cancer mortality was lower in diabetics receiving metformin (vs. sulfonylureas or insulin, HR 0.50-0.77), but they did not study diabetics not receiving any drug therapy. Furthermore, while confirming lower cancer risk in diabetics receiving metformin (versus those not receiving metformin). Finally, Libby et al. have reported a significantly reduced risk of incident cancers (HR 0.63, 95% CI 0.53-0.75) in diabetics receiving metformin (versus those not receiving metformin); they recommended a randomized trial be conducted to "assess whether metformin is protective in a population at high risk for cancer". Although many preventative agents have been or are being explored in NSCLC, such as sulindac, celecoxib, selenium, and others, none to date have shown proven benefit.

#### Metformin for non-small cell lung cancer

Large, phase III randomized studies for evaluating the effects of metformin as a chemoprevention agent are already underway in breast cancer. Although preliminary data suggests a potential effect in non-small cell lung cancer (Memmott RM et al., 2010), no trials addressing the question are yet open and enrolling. The recurrence rate for treated NSCLC ranges from 30-70% based on clinical and pathologic stage. For patients in the Stage IB-IIIA stage categories, adjuvant platinum-based chemotherapy has shown proven benefit with an increase in 5 year survival of 5-13%. Despite this improvement, recurrence rates remain high. Preliminary data has suggested activity of metformin in reducing cancer risk. Because metformin is a generic, inexpensive, well known and generally well tolerated oral agent that is commonly used to treat diabetes (including lung cancer patients who have diabetes), its evaluation as a potential adjuvant treatment for NSCLC can take place in an accelerated fashion. As lung

squamous cell carcinoma commonly affects the proximal airways, in contrast to lung adenocarcinoma, which typically affects more distal airway-alveolar units, the potential to bronchoscopically survey for precursor lesions such as bronchial dysplasia or carcinoma in-situ is feasible. Given this, we will institute the described pilot study protocol to evaluate the feasibility of metformin administration and tissue collection and to characterize the genomic alterations associated with these disease phenotypes under the influence of metformin administration. Interestingly, metformin has been linked to a number of the newly-identified genes identified with significant mutations in lung squamous cell carcinoma, including PTEN, PIK3CA, TP53, TSC1, BRAF, Notch1 and CREBBP. Whether metformin modifies the functional outcome for any of the novel mutations identified in invasive lung squamous cell carcinoma will be addressed in this pilot study.

#### Genomic alterations in the development and progression of NSCLC

A convergence of the ongoing rapid decrease in cost combined with increases in throughput for massively parallel sequencing technologies have set the stage for an exponential increase in the amount of detailed tumor sequencing data available. Pending results from the NCI sponsored TCGA projects in addition to other large-scale sequencing efforts for NSCLC will no doubt shed further light on recurring mutations in NSCLC and relevant molecular subtypes. DNA sequencing of NSCLC has been incredibly productive to date. The potential for EGFR-directed therapy in lung adenocarcinoma was originally described by Paez et al. (2004), in a project sequencing the activation domain from numerous tyrosine kinase receptors in the human genome from NSCLC tumor specimens. Through this work and other studies (Lynch et al., 2004), mutations in EGFR were discovered that correlated with response to gefitinib, and the era of targeted therapy for lung adenocarcinoma was born. EGFR-directed tyrosine kinase inhibitors such as erlotinib and gefitinib have now been studied extensively in a number of large international clinical trials, demonstrating equivalence with platinum-based chemotherapy for patients harboring sensitizing EGFR mutations (Mok et al., 2009). In a similar manner, EML4/ALK translocations were discovered by sequencing an expression library from a surgically resected lung adenocarcinoma specimen. Soda and colleagues (2007) found an inversion within chromosome 2p that leads to the formation of a fusion gene comprising portions of the echinoderm microtubule-associated protein-like 4 (EML4) gene and the anaplastic lymphoma kinase (ALK) gene. Functional studies in mouse NIH3T3 cells demonstrated that forced expression of this human fusion tyrosine kinase generated transformed foci in culture and subcutaneous tumours in nude mice. Data suggest that patients who harbor this mutation do not benefit from treatment with EGFR-kinase inhibitors, but do show sensitivity to ALK inhibition. Recent clinical studies have shown that patients with EML4-ALK fusion NSCLC have a better overall survival with crizotinib treatment, a novel ALK inhibitor, than with standard platinum-based chemotherapy (Shaw et al., 2011).

Despite these dramatic advances, little is known about precursor lesions for NSCLC. Adenocarcinoma in situ (AIS) remains a poorly understood entity from the standpoint of genomic alterations. The availability of well-characterized biospecimens for genome sequencing studies has hampered efforts in understanding this presumed precursor lesion for lung adenocarcinoma. Lung squamous cell carcinoma, in contrast, has a readily accessible precursor lesion termed bronchial dysplasia. Bronchoscopic studies of patients with NSCLC show a high frequency of bronchial dysplasia and carcinoma in situ. No detailed genomic characterization of

such lesions has yet been performed. Targeted agents which have been developed for the treatment of lung adenocarcinoma are largely ineffective for lung squamous cell carcinoma. The underlying genomic alterations in lung SCC are poorly described, and no targeted agents are currently approved for the treatment of lung SCC.

#### Metformin pharmacogenomics using patient-derived iPS cells

A number of recent pilot chemoprevention trials in multiple tumor types have attempted to show signals for specific agents by applying them first against established, invasive tumors. The validity of this strategy in identifying chemoprevention agents remains to be determined. A contrarian view holds that such a strategy will never accurately identify true chemoprevention agents. Histologically normal bronchial airway epithelia represent the field within which pre-invasive and then invasive malignancy develops in lung SqCC, and these cells represent the true target tissue for chemoprevention strategies in this disease. Assessing “response” however in the absence of a target lesion remains elusive. A further potential flaw in standard chemoprevention approaches is the unlikely possibility that all patients will show equivalent responsiveness to a specific strategy. Correctly identifying “responders” and “non-responders” to most chemoprevention agents has not been feasible, but may represent a crucial link to finding successful approaches. For example, recent data have suggested that LKB1 (STK11) mutations may influence responsiveness to either metformin or phenformin *in vitro* (Shackelford et al., 2013). Such genotypes in developing tumors might account for some of the heterogeneity in metformin responsiveness that has been observed in epidemiological studies across multiple tumor types.

Since the discovery of induced pluripotent stem cells (iPSCs) in 2007, this technology has been used to model diseases, interrogate drug response and toxicity, and create multiple differentiated cell types in unlimited quantity to evaluate potential for therapeutic transplantation (Yamanaka, 2012). Through ectopic expression of a series of pluripotency transgenes in somatic cells, specifically Oct4, Sox2, Nanog, and c-Myc, these cells develop properties similar to embryonic stem cells, with the ability to self-renew and differentiate into any cell population from all 3 primary germ layers (Takahashi et al., 2007). Because this technology does not involve embryo destruction, it bypasses the ethical controversies associated with derivation of traditional embryonic stem cells. In addition to the compelling possibility of using iPSCs for therapeutic transplantation, there is a growing realization that *in vitro* pharmacogenomic studies may be an important application. Patient-derived iPS cells have been utilized to evaluate the pharmacogenomics of drug response in a growing number of disease and organ models. This principle has been applied to study cardiotoxicity, hepatotoxicity, and other pharmacogenomic paradigms in a patient, cell type and disease-specific context not feasible using other systems (Liang et al., 2013 and Medine et al., 2013). Patient-specific iPS cells and their differentiated progeny may represent a new model for personalized medicine, with the ability to exhibit “patient in a dish” disease phenotypes or drug responses (Mordwinkin, et al., 2013). This model system represents unexplored potential to evaluate patient-specific responsiveness in chemoprevention.

## 1.2 Dose Rationale and Risk/Benefits

Metformin is mainly associated with gastro-intestinal side effects. Previous trials have been done comparing metformin to a placebo that provided information about the frequency and magnitude of the main side effects and the contribution of GI symptoms to dropout rates. It was found that gastrointestinal toxicity occurred more frequently in patients receiving metformin than placebo. However lower doses of metformin (our dose is 1700mg/day) lead to less drop out than doses  $\leq$  2000mg/day. All patients are unlikely to respond equally to the chemoprevention effects of metformin. Evaluation of metformin response in vitro using lung epithelial cells derived from iPSCs offers a model to develop strategies for individualized chemoprevention.

## 2 Study Objectives

Primary objective for pilot study:

1. To evaluate the feasibility of patient randomization, accrual, and tissue collection in a pilot study of metformin versus observation following resection of stage IA-IIIA lung squamous cell cancer for patients.
2. To compare the 2-year recurrence free survival (RFS) rate between metformin and observation.

[figure not shown]
Secondary objective(s) for pilot study:

1. To develop the metformin sensitivity index based on iPS cell lines from the first 20 patients randomized to the metformin arm.
2. To apply the metformin sensitivity index on the remaining 25 patients randomized to metformin and the 45 observation patients (70patients total) to compare the 2-year RFS rate between metformin-sensitive and metformin-not-sensitive patients
3. To compare adverse events between metformin and observation arms using CTCAE version 4.

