## 3 Study Design

### 3.1 General Design

Patients will be identified and enrolled from Thoracic Surgical Clinics. Patients will undergo surgical resection with the collection of tumor tissue, normal lung tissue, blood, and skin biopsies. For patients enrolled in the study that were found to have stage IA-IIIA SCC, starting less than 90 days from the time of surgery, patients will be randomized to receive either 850 mg po BID of metformin or observation. Metformin dosing will include a 4 week ramp up of 850 mg po daily prior to starting the BID dose, for a total of 6 months of Metformin. Patients will be followed for 2 years from the time of surgery to evaluate 2-year RFS. We plan to randomize a total of 100 patients (50 per arm), such that 90 patients are evaluable for the primary endpoint.

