## 7 Statistical Plan

### 7.1 Statistical Methods

All patients meeting the eligibility criteria, and who started treatment, will be considered evaluable for the 2 year RFS rate endpoint. The proportion of 2 year RFS rates (along with the 95% confidence interval) will be estimated within each arm by the number of patients who are recurrence-free and alive at 2 years divided by the total number of evaluable patients in each arm, and compared using a chi-squared test.

Clinical data regarding recurrence-free survival (RFS) will be utilized for development of the metformin sensitivity index. Data collected will be summarized using descriptive statistics, including mean and standard deviation and median and inter quartile range for continuous variables, and using frequencies and percentages for categorical variables. Logistic regression models will be used to assess the impact of metformin sensitivity index metrics, treatment, and the interaction between the metformin sensitivity index metrics and treatment on the 2 year RFS status as the outcome of interest.

Adverse events (AEs) will be compared between metformin and placebo using CTCAE version 4. To evaluate the AE profiles associated with each intervention arm, the maximum grade for each type of AE will be recorded for each participant and frequency tables will be reviewed to determine the overall patterns. The number and severity of AEs (overall and by intervention group) will be tabulated and summarized across all grades. Chi-square tests will be used to compare the AE rates between metformin and placebo.

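### Secondary objective 2 compares index-sensitive with index-not-sensitive patients across both arms, a contrast that mixes prognosis with metformin sensitivity; the Section 7.1 interaction that separates them is not tied to the objective

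*Combined protocol and SAP*

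**What the plan says.** Section 2 sets out two linked secondary objectives. The first develops the index "based on iPS cell lines from the first 20 patients randomized to the metformin arm". The second applies it to the "remaining 25 patients randomized to metformin and the 45 observation patients (70patients total") in order "to compare the 2-year RFS rate between metformin-sensitive and metformin-not-sensitive patients". The contrast named is one index group against the other. Neither treatment arm nor interaction is mentioned.

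Section 7.1 adds two things. RFS enters the making of the index: "Clinical data regarding recurrence-free survival (RFS) will be utilized for development of the metformin sensitivity index". Logistic regression is also planned for the index metrics, treatment, and "the interaction between the metformin sensitivity index metrics and treatment on the 2 year RFS status as the outcome of interest". That sentence does not say which objective the model serves, which of its terms decides the question, or which patients are in it.

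**The concern.** An index can relate to RFS in two ways. A prognostic index marks patients who do better whatever they receive. A predictive index marks patients who gain more from metformin. Only the second deserves the name sensitivity index. A comparison of the two index groups over a mixed set of treated and untreated patients returns a blend of both.

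The way the index is built makes the distinction matter more. All 20 development patients are on metformin and RFS data are used. Within that set, a patient who did well because of metformin looks the same as one who would have done well anyway. The application step is therefore where the two must be told apart, and the contrast written into objective 2 does not do it.

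The Introduction says the pilot is to inform a phase III decision, support a correlative grant and lead to a metformin response index. If objective 2 were analysed literally, a truly predictive index could look weak and a merely prognostic one could look validated.

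**Working it through.** **Inputs from the documents.** Development set: 20 metformin patients. Application set: 25 metformin plus 45 observation (Section 2). Section 3.1: "We plan to randomize a total of 100 patients (50 per arm), such that 90 patients are evaluable for the primary endpoint".

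**Inputs not in the documents.** No alpha is given for this objective; Section 7.1 mentions only a 95% interval for the arm-specific rates. No 2-year RFS rate, target effect, index cut-point or index-sensitive share is stated. The nearest figure is in the Background: "The recurrence rate for treated NSCLC ranges from 30-70% based on clinical and pathologic stage". That is a recurrence rate by stage, not a 2-year RFS rate. I assume two-sided 0.05, the same index-sensitive share in both arms (50%, range 30–70%), and the RFS values shown below.

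**1. The plan's counts reproduce.** 20 + 25 = 45 metformin; 45 + 45 = 90 evaluable; 25 + 45 = 70 in the application set. Observation share: 45/70 = 64.3%. Metformin share: 25/70 = 35.7%.

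**2. What the pooled contrast estimates.** Let G be the prognostic gap between index groups, the same in both arms, and D the extra gain from metformin in sensitive patients. Then pooled difference = G + (25/70) × D. This is one equation with two unknowns, so different truths give the same answer:
- Predictive only (sensitive patients on metformin go from 0.60 to 0.88): sensitive group = (25 × 0.88 + 45 × 0.60)/70 = 49/70 = 0.70, against 0.60.
- Prognostic only (0.70 vs 0.60 in both arms): 0.70 against 0.60.

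A larger sample would not resolve this.

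**3. Predictive-only index, D = 30 points, base 0.50.** Sensitive group = (25 × 0.80 + 45 × 0.50)/70 = 42.5/70 = 0.607. Pooled difference = (25/70) × 30 = 10.7 points. The exact rejection rate of a chi-squared test, 35 vs 35, is 13.5%.

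**4. Prognostic-only index, true interaction zero.** Exact chi-squared rejection rates for the pooled contrast:

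| RFS, sensitive vs not | 50% sensitive (35 vs 35) | 30% or 70% sensitive |
|---|---|---|
| 0.65 vs 0.50 | 23% | 21% |
| 0.70 vs 0.50 | 40% | 33–35% |
| 0.75 vs 0.45 | 74% | 66–67% |

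**5. The interaction in the same 70 patients** (difference of differences, Wald test, risk-difference scale). In the scenario of step 3, the metformin cells hold 12.5 each and the observation cells 22.5 each:

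SE = √[0.80 × 0.20/12.5 + 0.50 × 0.50 × (1/12.5 + 1/22.5 + 1/22.5)] = √(0.0128 + 0.0422) = 0.235.

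95% CI half-width = 1.96 × 0.235 = 0.46. With 0.30/0.235 = 1.28, power is about 25%. For smaller gains of 0.20–0.25, base RFS 0.30–0.70 and index-sensitive share 30–70%, power is about 12–24%. The interaction detectable with 80% power, taking a common RFS of 0.30–0.70 in all four cells, is about 0.64–0.76.

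**The case against.** The strongest reply is that the plan already contains the right analysis. The interaction model is the only method in Section 7.1 that relates the index to RFS. The two chi-squared comparisons there are between arms, for RFS and for adverse events. No test of a pooled index contrast is specified anywhere. Read together, objective 2 could be the aim and the interaction model the method.

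Much of this stands, and it rules out several stronger readings that a reader might infer:
- That the plan has no means of separating prognosis from sensitivity. It has one; the link to the objective is what is missing.
- That including 45 untreated patients is itself a mistake. They are the comparator the interaction needs. Restricting the comparison to the 25 metformin patients would not separate prognosis from sensitivity either.
- That the index is merely a fitted risk score. Section 2 rests it on iPS cell lines, and Section 1.2 describes in vitro metformin response. RFS data are used as well, so a prognostic component is possible but not established.
- That a prognostic index would necessarily be reported as a sensitivity index. That supposes the interaction is ignored, which the documents do not say.

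It is also fair that the 74% figure depends on a large assumed gap, and that moving to the interaction improves interpretation far more than power.

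The reply does not supply what Section 7.1 leaves open. An analyst could follow objective 2 to the letter, report the pooled difference and stay within the plan. An analyst fitting the Section 7.1 model could include the 20 development patients and stay within it too.

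**Conclusion.** The point holds as a mismatch between objective and analysis in a secondary objective of a pilot. As worded, the objective 2 contrast blends prognosis with metformin sensitivity. The term that separates them is planned but is not attached to the objective, not named as deciding, and not limited to the 70 patients outside the development set.

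The qualitative conclusion needs no assumed rate; step 2 of the working is enough. The size does depend on assumptions: a predictive effect keeps 35.7% of its magnitude in the pooled contrast if the index-sensitive share is equal across arms, and the chance of a false signal from a prognostic index ranges from about 21% to 74% over the gaps and shares considered. This should be changed because it governs what may be claimed about the index, and the change costs almost nothing.

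**What to change.** Restate secondary objective 2 as the difference in metformin effect on 2-year RFS (metformin minus observation) between index-sensitive and index-not-sensitive patients. In Section 7.1, state that:
- the index-by-treatment interaction is the term that addresses this objective;
- it is estimated only in the 70 patients not used to develop the index;
- it is reported as an estimate with a 95% CI, on a named scale (the logistic model gives a ratio of odds ratios; the illustration above uses risk differences);
- 2-year RFS is shown by index group separately within each arm;
- the pooled sensitive versus not-sensitive contrast is not used as evidence of metformin sensitivity.

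Keep the observation patients in the analysis.

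The cost is wording only: no added patients, samples or visits. The downside is that the interaction will be imprecise, with about 25% power for a 30-point effect and a CI half-width of about 0.46. The result should be labelled exploratory, and a non-significant interaction should not be read as showing that the index has no predictive value.
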